4. INTRODUCTION

4.1 Background

Hemodynamic optimization of critically ill patients is a goal for clinicians in order to afford the patient the best possible outcomes. Being able to precisely and rapidly determine patient fluid responsiveness provides the bedside physician and nursing staff the information needed to make critical decisions in regards to the patient's fluid status and management of additional fluids and medications. Patient management in the ICU is complex and multiple studies and meta-analyses have shown that clinicians struggle to diagnose which patients will benefit from fluid administration (i.e. the administration of intravenous fluids will increase cardiac output).¹ The findings show that up to 50% of patients in the ICU will not benefit from fluid administration.² Studies have also shown that excessive fluid administration and fluid retention leads to poorer outcomes.³⁻⁵ Well-timed decision making with accurate information is critical and challenging particularly in the setting of a patient with sepsis.

As fluid management and cardiac output determination are linked to better decision-making and improved outcomes in ICU, the use of a dynamic assessment of fluid responsiveness becomes a key tool for patient management. The Noninvasive Starling SV device, which is FDA cleared and CE marked, is currently in clinical use and can be used to provide a dynamic assessment of fluid responsiveness. This study will show the clinical utility of initiating an assessment of patient fluid responsiveness prior to the administration of treatment fluid.

5. STUDY JUSTIFICATION

This study is designed to highlight the benefits of treatment guided by dynamic measures using the Starling SV within the population of patients diagnosed with sepsis and refractory hypotension. To confirm this, treatment and outcome data will be compared between patients randomized to receive treatment guided by a dynamic assessment of fluid responsiveness, compared to the current standard of care treatment.

6. DEVICE

6.1 Device Description

Cheetah Medical's Noninvasive Starling SV is a portable, non-invasive, cardiac output detector system. The Starling SV system measures the cardiac output by employing electrical bioimpedance. Bioimpedance is a measure of the electrical characteristics of a volume of tissue and fluid. In the case of cardiac output measurements, the relevant tissue includes the heart and the immediate surrounding volume of the thorax. The relevant fluid is blood.

Cheetah Medical's Starling SV electrode is a double electrode sensor. Within each sensor, one electrode is used to transmit a high frequency sine wave into the body, while the resulting voltage is measured at the adjacent electrode. Four electrodes are placed at specific areas of the thorax, the impedance to the current flow calculated, and the electrical bioimpedance waveform constructed. This information is used to determine cardiac output. The Starling SV device also measures and displays associated hemodynamic parameters based on calculations of measurements already incorporated into the Starling SV device. These parameters are: Cardiac Index (CI), Ventricular Ejection Time (VET), Total Peripheral Resistance Index (TPRI), Stroke Volume Index (SVI), Stroke Volume Variation (SVV), Cardiac Power (CP), Cardiac Power Index (CPI) and Thoracic Fluid Content (TFC). Fluid responsiveness is indicated by a change in SV of $> +10\%$ in response to a fluid challenge.⁶

6.2 Device Accountability

The Starling SV system (monitor and electrode disposables) will be supplied by Cheetah Medical to each investigational site.

6.3 Device Indication for Use

The Starling SV with NIBP and SpO₂ functionalities is a portable, hemodynamic monitoring non-invasive Cardiac Output monitoring device that monitors and displays a patient's Cardiac Output (CO) in Ltr/Min with a Non Invasive Blood Pressure (NIBP) function that non-invasively measures and displays blood pressure (diastolic, systolic and mean arterial pressure) and heart rate and with a SpO₂ function that non-invasively measures and displays blood oxygen saturation (SpO₂). The device displays associated hemodynamic parameters based on measurements or calculations of measurements already incorporated into the Starling SV. These parameters are:

- Cardiac Index (CI),
- Stroke Volume (SV),
- Stroke Volume Index (SVI),
- Stroke Volume Variation (SVV),
- Heart Rate (HR),
- Ventricular Ejection Time (VET),
- Total Peripheral Resistance (TPR),
- Total Peripheral Resistance Index (TPRI),
- Cardiac Power (CP),
- Cardiac Power Index (CPI),
- Blood Oxygenation (SPO₂)
- Oxygen Delivery Index (DO₂I),

- Electrical impedance of the chest cavity (Z0),
- Thoracic Fluid Content (TFC),
- Thoracic Fluid Content change from preset time period (TFCd) and
- Thoracic Fluid Content from baseline (TFCd0).
- Changes in SV, CO and other hemodynamic parameters which are derived by Bioreactance® as a result of posture

The Starling SV with NIBP and SpO2 functionalities is intended for use within hospitals and other healthcare facilities (e.g., outpatient clinics) that provide patient care).

6.4 Device Procedure(s)/Training

All sites will receive device training on the Cheetah Starling SV system prior to study initiation.

6.5 Fluid Assessment-Passive Leg Raise (PLR)

The passive leg raise (PLR) shall be followed according to the following guidelines:

- Select PLR Test from main menu on Starling SV system
- With patient in semi-recumbent position (30-45°), obtain three minutes of monitoring for average baseline SVI
- With patient legs raised to 45 degree angle, obtain three minutes of monitoring for peak SVI value
- Fluid responsiveness is indicated by a $\Delta \text{SVI} \geq +10\%$

7. INVESTIGATIONAL DESIGN

7.1 Study Objective

The objective of this study is to assess the mean difference in fluid balance at 72 hours or ICU discharge, whichever occurs first, and associated patient outcomes, based on a dynamic assessment of fluid responsiveness in septic patients with refractory hypotension in an ICU setting.

7.2 Study Design

This study is a prospective, multi-center, randomized trial comparing the mean difference in fluid balance and associated patient outcomes between a treatment guided by a dynamic assessment of fluid responsiveness and a standard of care control group not using dynamic fluid assessment. Between seven and fifteen sites will be used to enroll 210 subjects with the diagnosis of sepsis and refractory hypotension and in whom the Starling SV system can be attached. Subjects will be randomized in a 2:1 treatment to control group ratio. In the treatment group, a dynamic assessment of fluid responsiveness will be performed at every clinical decision point to treat hypoperfusion or impending hypoperfusion for the first 72 hours of study enrollment. Examples of a clinical decision point include a MAP of < 65, SBP < 90 or blood pressure that is rapidly trending lower, low urine output, or any other clinical indication to administer/alter fluid bolus or pressors. Additionally, an assessment of fluid responsiveness will be performed every 12 hours if no clinical assessments have taken place during this time period.

Fluid responsiveness will be assessed using a passive leg raise (PLR) to guide corresponding treatment (**Appendix A**). Continuous data will be collected from the Starling SV system during the entire treatment period. In the control group, no required therapeutic protocol will be used for patient treatment, and is determined per the discretion of the physician and hospital standards. The use of dynamic fluid assessment (i.e. SVV, PPV, or SV change) to determine fluid responsiveness within the control group is prohibited.

7.3 Study Endpoints

7.3.1 Primary Endpoint

The primary endpoint is an evaluation of the difference (L) between the two treatment groups mean fluid balance at 72 hours or ICU discharge, whichever occurs first. The following hypothesis will be tested:

$$H_a: \mu_c - \mu_T \neq 0$$

where μ_T and μ_c is the average fluid balance in the Starling SV and control groups, respectively.

7.3.2 Secondary Endpoints

Secondary endpoints to be evaluated:

1. Length of ICU stay (days) until subject is medically ready for discharge
2. Number of hours free from ventilator use
3. Requirement for mechanical ventilation
- 4.
5. Number of hours free from vasopressor use
6. Changes in serum creatinine levels from baseline
7. Requirement for renal replacement therapy (RRT)
8. Mean volume of fluid between the two treatment groups
9. Incidence of Major Adverse Cardiac Event (MACE)
10. Incidence of Adverse Events (AE)
11. Number of ICU readmissions
12. 30 day in-hospital Mortality rate
13. Discharge location
14. Mean difference in fluid balance at ICU discharge

7.4 Study Duration

Estimated Study Start:	Q3 2016
Estimated Enrollment Completion:	Q2 2018
Estimated Final Report:	Q3 2018

8. SUBJECT POPULATION AND SELECTION

8.1 Subject Population

[figure not shown]
Adult subjects with the diagnosis of sepsis and refractory hypotension will be considered as a candidate for the study. A maximum of 210 subjects enrolled and in the analysis population will be included in the study. Subjects will be considered to be enrolled when they or their designated representative sign the informed consent form (ICF).

Subjects who are enrolled will be assigned a subject ID. Subjects that sign the ICF, but are found ineligible will be considered screen failures and will be exited from the study at that time. Enrolled subjects who meet study eligibility will be included in the analysis populations and are further described in **Section 12**.

The diagnosis of sepsis is defined as a known or presumed infection and the presence of 2 or more SIRS criteria as detailed in **Section 8.2**. Refractory hypotension is defined as the presence of hypotension following initial resuscitation with 1L of fluid. After obtaining ICF and confirming that the inclusion and exclusion criteria are met, the Cheetah sensors will be placed and connected to the Starling SV monitor. Useable readings will be confirmed prior to initiating the study data collection period.

A diagram outlining the overall subject enrollment plan is shown below:

Figure 1: Subject Flow Diagram

8.2 Inclusion Criteria

Subjects must meet the following inclusion criteria:

1. Diagnosis of sepsis, as exhibited by 2 or more of the following SIRS criteria and a known or presumed infection at the time of screening:
 - Temperature of $> 38\text{ C}$ or $< 36\text{ C}$
 - Heart rate of $> 90/\text{min}$
 - Respiratory rate of $> 20/\text{min}$ or $\text{PaCO}_2 < 32\text{ mm Hg}$ (4.3 kPa)
 - White blood cell count $> 12000/\text{mm}^3$ or $< 4000/\text{mm}^3$ or $> 10\%$ immature bands
2. Refractory hypotension (either one single reading of MAP < 65 exhibited during the evaluation period, or requiring treatment with vasopressors to maintain a MAP > 65) despite initial fluid resuscitation (1L of treatment fluid)
3. Patient enrolled in study within 24 hours of arrival to the hospital
4. Anticipated ICU admission. Patients may be maintained on another unit (such as within the ER or a step down unit) during the 72 hour monitoring period if the treatment algorithm is adhered to during this time period.
5. Able to provide signed informed consent or consent can be obtained from the patient's authorized representative

8.3 Exclusion Criteria

Subjects must not have any of the following exclusion criteria:

1. Primary diagnosis of: acute cerebral vascular event, acute coronary syndrome, acute pulmonary edema, status asthmaticus, major cardiac arrhythmia, drug overdose, or injury from burn or trauma
2. Known aortic insufficiency, or aortic abnormalities
3. Hemodynamic instability due to active hemorrhage, (e.g. gastrointestinal bleeding/coagulopathy/trauma)
4. Patient has received > 3 liters of IV fluid prior to study randomization
5. Requires immediate surgery
6. Patient transferred to the ICU from another hospital unit
7. Do not attempt resuscitation (DNAR or DNR) order
8. Advanced directives restricting implementation of the resuscitation protocol
9. Contraindication to blood transfusion
10. Attending clinician deems aggressive resuscitation unsuitable
11. Transferred from another in-hospital setting
12. Not able to commence treatment protocol within 1 hour after randomization
13. Known intraventricular heart defect, such as VSD or ASD
14. Use of additional hemodynamic monitoring involving SVV, PPV or SV changes to determine fluid responsiveness
15. Seizure in the last 24 hours
16. Prisoner
17. Pregnancy

18. Age <18
19. Known allergy to sensor material or gel
20. Inability or contraindication to doing a passive leg raise with both extremities, such as inability to interrupt venous compression boots
21. Patient has an epidural catheter in place
22. Suspected intra-abdominal hypertension
23. Inability to obtain IV access
24. Diabetic ketoacidosis
25. Hyper-osmolarity syndrome
26. Patient treatment uncouples from the treatment algorithm

27. Patient should be excluded based on the opinion of the Clinician/Investigator

8.4 Subject Screening

All subjects diagnosed with sepsis and refractory hypotension will be considered potential candidates. All subjects screened for the study will be captured on the site's Screening Log. The log will capture the subject's gender, age, date of screening and the reason(s) for study exclusion.

8.5 Informed Consent Procedures

Written informed consent on the approved IRB informed consent form must be obtained for all subjects who are potential study candidates before any study specific tests or procedures are performed. Due to the high likelihood of the subject's critical clinical state and therefore the possibility of their inability to provide informed written consent, the subject's designated representative will be acceptable to provide written informed consent.

The general process for obtaining informed consent shall:

- Ensure that the principal investigator or his/her authorized designee conducts the informed consent process;
- Include all aspects of the clinical investigation that are relevant to the subject's decision to participate throughout the clinical investigation;
- Avoid any coercion or undue improper influence on, or inducement of, the subject to participate;
- Not waive or appear to waive the subject's legal rights;
- Use native non-technical language that is understandable to the subject;
- Provide ample time for the subject, or designee, to read and understand the informed consent form and to consider participation in the clinical investigation;
- Include personally dated signatures of the subject and the principal investigator or an authorized designee responsible for conducting the informed consent process;
- Provide the subject, or designee, with a copy of the signed and dated informed consent form and any other written information required per Site's Institutional Policy (i.e. additional HIPAA language).

8.6 Subject Randomization

Subjects will be randomized to either the treatment or control arm of the study once the decision has been made to admit the patient to the ICU. Any patients that are enrolled but are not admitted to the ICU, or who receive > 3L of treatment fluid prior to randomization will be considered a screen failure and will be exited from the study at this time.

Subjects will be randomized in a 2:1 treatment to control ratio to increase power for sub-analysis by patient population. Additionally, subject randomization will be stratified to ensure even randomization between the three time windows of enrollment (0-6 hours, 6-12 hours, 12-24 hours)

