### 6.2 INTENT TO TREAT POPULATION (ITT)

The intent-to-treat (ITT) population for this study includes subjects that are enrolled in the study, have signed the ICF, meet study eligibility criteria, and have been randomized to either the treatment or control arm of the study.

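### Exclusions 12 and 26 describe events after randomisation, yet ITT, mITT and (through ITT) Safety require eligibility, so randomised patients can be dropped for what happens after allocation

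*Protocol*

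**What the plan says.** **Timing.** Protocol 8.6 randomises patients "once the decision has been made to admit the patient to the ICU", that is, at the decision and not at arrival in the unit. Protocol 8.1 counts a patient as enrolled from signature of the consent form, and exits as screen failures those who signed but prove ineligible.

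**Eligibility list.** Protocol 8.3 includes exclusion 12, "Not able to commence treatment protocol within 1 hour after randomization", and exclusion 26, "Patient treatment uncouples from the treatment algorithm". Protocol 7.2 leaves control treatment to the physician and hospital standards, with no prescribed therapeutic protocol.

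**Analysis sets.** SAP 6.2 limits ITT to patients who "meet study eligibility criteria, and have been randomized to either the treatment or control arm of the study". Protocol 12.2.2 sets the same condition, and both mITT definitions (Protocol 12.2.3, SAP 6.3) repeat it. Per-protocol (Protocol 12.2.4, SAP 6.4) asks only for critical eligibility criteria. SAP 6.5 takes Safety from ITT. SAP section 9 runs efficacy on per-protocol (primary) and mITT (supportive). SAP section 10 runs adverse events on mITT and Safety.

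**ICU admission.** Protocol 8.6 makes screen failures of "Any patients that are enrolled but are not admitted to the ICU". Inclusion 4 (Protocol 8.2) asks only for anticipated ICU admission and adds: "Patients may be maintained on another unit (such as within the ER or a step down unit) during the 72 hour monitoring period".

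**The concern.** An intention-to-treat set protects the comparison because membership is settled at allocation. Here membership depends on a list with at least one item that can be observed only while treatment is under way. Leaving the algorithm may well reflect how the patient responded or deteriorated. If those patients are removed from one arm, the groups compared are no longer the groups randomised.

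Safety is exposed as well. A Starling patient whose care departs from the algorithm could be found ineligible, fall out of ITT, and so fall out of the Safety set and the adverse event tables.

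The ICU rule raises a related doubt. Randomisation comes at the decision to admit, so non-admission can become known afterwards, and a patient kept in the ER or a step-down unit under inclusion 4 is literally not admitted to the ICU. Nothing in the documents mentions blinding of treating staff, so sites could apply an unclear rule knowing the arm.

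**Working it through.** **1. When each rule can be judged, and in which arm**

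| Rule | When it is known | Arms it can act on |
|---|---|---|
| Exclusion 26 | Only during treatment | Starling only, since Protocol 7.2 sets no protocol for control |
| Exclusion 12 | Read literally, up to 1 hour after randomisation; could be applied as a forecast | Either, though only Starling has a defined protocol to start |
| 8.6, not admitted to the ICU | Unclear: before or after randomisation | Both |
| 8.6, more than 3 L of fluid | Before randomisation | Both; no difficulty here |

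**2. Which sets use the rule**

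- ITT and mITT, in both documents: all study eligibility criteria.
- Safety: ITT patients in whom study treatment was at least attempted, so it inherits the condition.
- Per-protocol: critical criteria only. Neither document says whether 12 or 26 is critical.

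As written, then, neither ITT nor mITT is guaranteed to hold every randomised patient, and no planned efficacy analysis is run on all randomised patients.

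**3. Internal check in the SAP.** SAP 7.4 tabulates protocol violations for the ITT set, and one violation type is enrolment without meeting the inclusion or exclusion criteria. SAP 6.2 has already removed those patients from ITT. Either that row is empty by construction or the ITT definition is not meant as written.

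**4. The plan's own power figure.** Inputs from Protocol 12.1 and SAP section 5: 80 and 40 patients, effect 2 L, SD 3 L, two-sided 0.05.

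- SE = 3 × √(1/80 + 1/40) = 0.581 L.
- Noncentrality = 2 / 0.581 = 3.44. The noncentral t with 118 degrees of freedom gives 92.7%, which agrees with the plan.

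**5. Illustration for exclusion 26 only.** The documents give no removal rate and no outcome for such patients, so both are assumed. Let a fraction f of the Starling arm be removed, with mean balance g litres above the mean of those who stay. The full-arm mean exceeds the retained mean by f × g, so removal moves the difference by f × g towards Starling.

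| f (removed of 80) | g | Shift = f × g | Share of planned 2 L |
|---|---|---|---|
| 5% (4) | 2 L | 0.10 L | 5% |
| 5% (4) | 4 L | 0.20 L | 10% |
| 10% (8) | 2 L | 0.20 L | 10% |
| 10% (8) | 4 L | 0.40 L | 20% |

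With SD 3 L and no true effect, the chance of a significant result favouring Starling is nominally 2.5%. In the first row SE = 3 × √(1/76 + 1/40) = 0.586, noncentrality 0.10/0.586 = 0.17, and the chance is 3.7%. In the last row SE = 3 × √(1/72 + 1/40) = 0.592, noncentrality 0.40/0.592 = 0.68, and the chance is 9.9%. If the removed patients have balances 2-4 L below the rest, the shifts reverse sign and the chance falls to 1.7% and 0.4%.

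Loss of numbers alone matters little: with 76 or 72 Starling patients and no outcome difference, power is 92.3% or 91.8%. The issue is bias, not power.

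**The case against.** **The ICU rule may act before randomisation.** A reader might infer that 8.6 removes randomised patients whom inclusion 4 accepts. The text does not establish this. Enrolled means consented, screen failure is the term Protocol 8.1 uses for consented patients found ineligible, and the same sentence's fluid condition, "who receive > 3L of treatment fluid prior to randomization will be considered a screen failure", is plainly pre-randomisation. One can read the whole sentence that way. What stands is an ambiguity between 8.6 and inclusion 4.

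**Not every set is shown to be affected.** It is tempting to say that these patients leave all the sets. Per-protocol asks only for critical criteria, so this is not shown for the analysis the SAP calls primary.

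**Eligibility may mean status at entry.** Table 1 determines eligibility before consent and Protocol 9.1 continues it at baseline. Exclusion 12 can be applied as a forecast of feasibility, and SAP 7.4 suggests that its authors expected some ineligible patients to remain in ITT. This is a fair defence of exclusion 12. It does not work for exclusion 26, which has no meaning before treatment starts, and the definitions nowhere say that eligibility is judged at entry.

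**The figures rest on assumptions.** This stands in full. They also fit only one-arm removal. Patients who recover early and never reach the ICU could come from both arms and might have lower balances; equal removal of similar patients from both arms gives no shift.

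**Redefining ITT alone changes no planned efficacy result.** True, because SAP section 9 uses per-protocol and mITT. The remedy has to reach mITT and Safety too.

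**Conclusion.** The point holds in a limited form. Exclusion 26, and exclusion 12 read literally, are post-randomisation events placed in the eligibility list. As ITT and mITT invoke that list and Safety is nested in ITT, randomised patients can be removed from the supportive efficacy analysis and from the safety analyses because of events after allocation, in the Starling arm only under exclusion 26. The one-arm conclusion rests on Protocol 7.2; the algorithm in Appendix A is not reproduced in the text available. SAP 7.4 does not fit the SAP's own ITT definition. Protocol 8.6 and inclusion 4 must be reconciled, but the documents do not show that 8.6 removes randomised patients.

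The size and direction of bias cannot be determined. The 0.1-0.4 L shift, 5-20% of the planned effect, is conditional on 5-10% removal under exclusion 26 and a 2-4 L excess. It should not be read as an estimate for this trial or as an error rate of its primary analysis. The correction is cheap and worth making.

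**What to change.** 1. Define ITT in both documents as all randomised patients, analysed as assigned, with no eligibility condition.
2. In mITT and Safety, judge any eligibility condition only on information available before randomisation. The Starling-only monitoring requirement in mITT is a separate matter that this wording does not address.
3. Record exclusions 12 and 26 as post-randomisation deviations, not eligibility failures, and state whether they count as major deviations for per-protocol. SAP 7.4 can then tabulate them in ITT without contradiction.
4. State that the 8.6 screen-failure rule covers only events before randomisation.
5. Reconcile 8.6 with inclusion 4, and say how the endpoint at 72 hours or ICU discharge is timed for a randomised patient who never enters the ICU.
6. Report the primary endpoint on the corrected ITT set, at least as a sensitivity analysis.

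The cost is wording in the protocol and SAP, collection of fluid balance to the endpoint in patients who would otherwise be exited, and slight dilution of the treatment effect because patients who left the algorithm are counted in their assigned arm.
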